**It is important, that VAS scores, ODI, ZCQ, and EQ-5D are filled in by the patient prior to walking distance test.**

- **Patient Satisfaction Questionnaire**  
Patients will be asked in a questionnaire for their subjective satisfaction with the result of the treatment (4 grading levels) and if they would again agree to a surgical treatment if they would have to make the decision again (yes / no).
- **Questionnaire about employment**  
Patients will be asked about their employment status, workman's comp status and treatment satisfaction.

#### Information of Patients on Questionnaires

All questionnaires and VAS will be explained to the patient extensively by the investigator. The patients will not have access to the questionnaires / VAS which they have filled in during prior visits. The questionnaires / VAS should be filled in by the patients themselves; they should not be influenced by the investigator or other persons.

#### **4.7.4. Direct Data Capture**

All documents that are used on site are considered source. All patient questionnaires are defined as direct data capture pages and they represent the source of the captured data (for monitoring they will be monitored as source data and there will be no other source for these data). The study coordinator will enter the source data onto the eCRF's. The monitors will verify the source documents match the eCRF's. Once this has been verified the data manager will lock the field so the data cannot be changed unless requested from the data manager.

The data will be entered into a validated electronic database capture (EDC) system: OpenClinica. The data manager will be responsible for programming of the database and data management. The Investigator or his/her designee is responsible for data entry at the time of the subject visit. The site CRA and data manager will review the data for completeness and accuracy compared to source documents (e.g., medical charts, hospital records, etc.). The CRA, data manager, or Sponsor can initiate queries where data is inconsistent or incorrect. Queries are entered, tracked, and resolved through the EDC system directly.

All procedures for the handling and analysis of data will be conducted using good computing practices meeting FDA guidelines for the handling and analysis of data for clinical trials.

#### **4.7.5. Neurological Status**

Neurological status will be evaluated by:

- Muscle strength (listed for nerve roots from L3, L4, L5, S1; scoring from 0 to 5)
- Sensory deficits (listed for nerve roots from L3, L4, L5, S1; defining status)
- Reflex
- Straight Leg Raise

#### **4.7.6. Walking Distance Test**

During this test a patient has to walk on a treadmill (speed 1.2 miles/hour) for 15 min. If the patient cannot keep up for the complete 15 min the maximum time that he was able to walk on the treadmill will be captured. The corresponding walking distance will be calculated.

The person conducting the walking test (i.e., physician, therapist, PA) must check whether a patient shows any medical symptom that contradicts an exercise test on the treadmill (e.g. heart problems). If the patient is not able to perform the walking distance test at any of the clinical visits it does not lead to exclusion for the study.

#### **4.7.7. Central Evaluation of Radiological Images**

Only sites with digital X-ray capability will enroll patients into this study.

---

 Deen H. et al., Measurement of exercise tolerance on the treadmill in patients with symptomatic lumbar spinal stenosis: a useful indicator of functional status and surgical outcome, J. Neurosurg 83:27-30, 1995

 Deen H. et al., Use of the Exercise Treadmill to Measure Baseline Functional Status and Surgical Outcome in Patients With Severe Lumbar Spinal Stenosis, Spine: Volume 23(2) 15 pp 244-248, 1998

In order to achieve a comparable evaluation, all radiological images will be evaluated by a core lab. For evaluation of X-rays a special form “core evaluation of X-rays” is available. All relevant parameters are listed in this special case report form.

X-ray images will be sent electronically to the core lab, either on a CD or via mail or via FTP site.

Anonymized electronic copies will be stored at sponsor and might be used for external reading and evaluation in the future.

Preoperative MRI images, 24 Month CT images, and 60 Month CT images for subjects with symptomatic, confirmed spinous process fracture will also be collected. Fractures are confirmed by the core lab.

#### **4.7.8. Assessment of Concomitant Medication:**

##### Pain Management

The investigator will ask the patient for detailed information on all pain killers taken. The type of pain killers used by the patient (Visit 1 – Visit 5) will be captured via the eCRF. It will be differentiated between the following types of pain killers: Class II narcotics, other narcotics (“Tramadol”, “Tilidin”), NSAIDs including acetylsalicylic acid (“Aspirin”) and acetaminophen (“Paracetamol”). It will be analyzed if pain killers were not used any more or if less strong pain killer classes are used. Other kind of pain management such as epidural steroid injection, facet injection or nerve root block will be documented in the eCRF (Visit 1, Visit 3, Visit 4, Visit 5, Visit 6, Visit 7, Visit 8).

##### Other Concomitant Medication

Concomitant medication will not be recorded except if they are related to an SAE or might have impact on the study evaluation according to the investigators decision.

#### **4.7.9. Physical Examination**

A detailed physical examination will be performed at Visit 1. In the following visits only a routine physical examination will be performed and changes compared to screening will be recorded. The investigator is free to perform a complete physical examination.

Medical history will be documented in the medical history form only. Medical history will be source verified through source document worksheets and medical records.

#### **4.7.10. Follow Up Treatment after Discharge**

There are no study related limitations to the routine follow up treatment (e.g., use of orthoses, physiotherapy). The follow up treatment will be recorded in the eCRF until Visit 8.

#### **4.7.11. Informed Consent**

Before any trial related action will be performed, a **written informed consent** will be obtained from each patient or the legal representative after adequate patient information; this includes the handing over of the written patient information and informed consent form that was approved by the IRB. During this procedure the investigator informs the patient extensively about all aspects of the trial. The patient will have an opportunity to ask questions.

## 4.8. Description of Study Visits

### 4.8.1. Visit 1: Screening (< 4 weeks before day 0)

This visit can be performed up to 4 weeks before day 0 (day of surgery) or even at the same day of surgery as long as the patient gets sufficient time to think over the study participation after being informed by the investigator.

- During the screening visit the **ODI**, **ZCQ**, **EQ-5D** and **VAS back pain** and **VAS leg pain** of the patient will be assessed as baseline level (baseline for ZCQ patient satisfaction is assessed at the first post-operative visit at visit 3 as these questions only concern post-operative aspects). A questionnaire about **status of employment / pension** will be filled in by the patient.
- Demographic and medical history data (including weight, height, race, etc.), data about **pain management** as well as a **physical examination** will be assessed as routinely done at each center.
- It will be documented in the eCRF which prior therapy had been performed for back- and leg-pain (epidural injection, facet injection, nerve root block).
- The **Body Mass Index** (BMI) will be determined by the investigator as this is one of the exclusion criteria. BMI = body weight: (body height in m). The unit of the BMI is kg/m^2.
- Only if all **in-/exclusion criteria** are fulfilled (as far as assessable before surgery) the patient will be considered for surgery. In case any in/exclusion criterion is not fulfilled prior to enrollment this patient will be judged as a screening failure and will not receive a patient number.
- For screening failures only the informed consent, patient identification data and the reason for failure will be monitored by the study monitor. Screen failures will be replaced by new patients in order to achieve 406 treated study patients.
- As baseline levels a **Walking Distance Test** will be performed and the **Neurological Status** will be assessed.
- **X-ray images** necessary for inclusion must be available in anterior-posterior position as well as in lateral position and in flexion and extension and should not be older than 6 months.

Images will be taken to evaluate in-/exclusion criteria (e.g. exclusion of isthmic spondylolisthesis or spondylolysis). Translatory instability has to be excluded utilizing functional X-rays ( $\leq 3$  mm).

All X-ray images are made in standing position.

- Necessary routine **MRI** (Post-Myelo-CT is also permitted in the event that the patient already has one that is  $<6$  months old) images must be available and should not be older than 6 months. They are obligatory for a clear definition of the medical indication (spinal stenosis) of the study patient. Further MRI imaging is not planned for this trial. The cross-sectional area of the spinal canal and foraminal area at the levels to be decompressed will be collected at baseline.

### 4.8.2. Visit 2: Surgery

- Completion of in/exclusion criteria
- Surgery
- Hospitalization information will be collected such as duration of surgery, blood loss and number of days in hospital.

- Discharge Information: Date of discharge, neurological status, pain management, follow-up treatment. X-rays have to be performed before discharge only in group B (with implant) in anterior-posterior and lateral position.
- Exclusion during the decompression surgery:  
In case the surgeon identifies during surgery any circumstance that contradicts to the patient's participation in the trial, the surgeon has to exclude the patient from the trial participation. Possible exclusion reasons are:
  - Instabilities assessed during surgery that requires stabilization by spinal fusion.
  - Partial resection or resection of disc tissue (see exclusion criterion 2).
  - (S)AEs assessed during surgery that rule out the implantation of coflex® (e.g. breakage of a spinal process, local osteoporosis).
- As these patients had been enrolled an eCRF will be filled in. The study monitor will only check the signed informed consent form and patient demographics as well as the reason of failure. The patient will be a dropout and the dropout reason will be recorded in the eCRF.

#### **4.8.3. *Visit 3: 3 months follow up (±2 weeks)***

- VAS leg pain
- VAS back pain
- Questionnaires ODI, ZCQ, EQ-5D, patient satisfaction, status of employment / pension
- Physical examination
- Neurological status
- Pain management
- Hospitalization
- Follow up treatment
- X-ray images for both groups in all four positions
- Walking distance test

#### **4.8.4. *Visit 4: 12 months follow up (±2 month)***

- VAS leg pain
- VAS back pain
- Questionnaires ODI, ZCQ, EQ-5D, patient satisfaction, status of employment / pension
- Physical examination
- Neurological status
- Pain management
- Hospitalization
- Follow up treatment
- X-ray images for both groups in all four positions
- Walking distance test

#### **4.8.5. *Visit 5: 24 months follow up (±2 month)***

- VAS leg pain
- VAS back pain
- Questionnaires ODI, ZCQ, EQ-5D, patient satisfaction, status of employment / pension
- Physical examination
- Neurological status
- Pain management
- Hospitalization

- Follow up treatment
- X-ray images for both groups in all four positions
- CT Scan for all subjects
- Walking distance test

**4.8.6. *Visit 6: 36 months follow up (±4 month)***

- VAS leg pain
- VAS back pain
- Questionnaires ODI, ZCQ, EQ-5D, patient satisfaction, status of employment / pension
- Physical examination
- Neurological status
- Pain management
- Hospitalization
- Follow up treatment
- X-ray images for both groups in all four positions
- Walking distance test

**4.8.7. *Visit 7: 48 months follow up (±4 month)***

- VAS leg pain
- VAS back pain
- Questionnaires ODI, ZCQ, EQ-5D, patient satisfaction, status of employment / pension
- Physical examination
- Neurological status
- Pain management
- Hospitalization
- Follow up treatment
- X-ray images for both groups in all four positions
- Walking distance test

**4.8.8. *Visit 8: 60 months follow up (±4 month)***

- VAS leg pain
- VAS back pain
- Questionnaires ODI, ZCQ, EQ-5D, patient satisfaction, status of employment / pension
- Physical examination
- Neurological status
- Pain management
- Hospitalization
- Follow up treatment
- X-ray images for both groups in all four positions
- CT Scan for symptomatic, confirmed spinous process fracture subjects
- Walking distance test

**4.8.9. *Common Events***

- Unscheduled Events – Visits that occur outside of the scheduled set of visits
  - VAS leg pain
  - VAS back pain
  - Questionnaires ODI, ZCQ, EQ-5D, and patient satisfaction
  - Walking-Distance Test

- Secondary Surgical Interventions (SSI)
  - VAS leg pain
  - VAS back pain
  - Questionnaires ODI, ZCQ, EQ-5D, and patient satisfaction
  - Walking Distance Test
  - SSI detail form
- Adverse Events (events occurring after the time of incision).

#### **4.8.10. Schedule of Study Visits**

A tabular summary of visit schedule is provided below.

Visits	Screening		Follow-Up						Final Report
	1 < 4 weeks before d0	2 day 0 surgery	3 months after surgery (±2 weeks)	4 12 months after surgery (±2 month)	5 24 months after surgery (±2 month)	6 36 months after surgery (±4 months)	7 48 months after surgery (±4 months)	8 60 months after surgery (±4 months)	
Patient information and Informed consent	X								
Demographics	X								
Medical history	X								
Pain management	X	X 	X	X	X	X	X	X	
Physical examination	X 		X 	X 	X 	X 	X 	X 	
Neurological status	X	X 	X	X	X	X	X	X	
Inclusion/exclusion criteria	X	(X)							
X-ray in standing position (AP, lateral, flexion, extension)	X	X 	X	X	X 	X	X	X 	
MRI and/or Post Myelo CT (not older than 6 months)	X								
Diagnosis	X								
Walking Distance Test (treadmill)	X		X	X	X	X	X	X	
VAS back pain, VAS leg pain	X		X	X	X			X	
ODI, ZCQ, EQ-5D	X		X	X	X	X	X	X	
Surgery		X							
Patient's satisfaction questionnaire			X	X	X	X	X	X	
Documentation of AEs		X	X	X	X	X	X	X	

1) A detailed physical examination will be performed at visit 1. In the following visits only a routine physical examination will be performed and changes compared to screening will be recorded. The investigator is free to perform a complete physical examination.

2) Only group B (with coflex® implant: anterior-posterior, lateral).

3) After surgery, before discharge.

4) CT Scans will be conducted at 24 months for all subjects and at 60 months for all symptomatic, confirmed spinous process fracture subjects.

#### **4.9. Device Accountability:**

The coflex® devices are marked with a lot number. An individual serial number is not available. For the trial routinely delivered coflex® devices that are available at each center are used. There will not be any trial specific device shipments and therefore device accountability will not be performed.

Charge number and size of the coflex® implants used with every study patient will be documented in the eCRF.

#### **4.10. Travel Cost Compensation:**

Every patient will receive travel cost compensation up to \$100 pending IRB approval. The travel expenses will be provided to the patient by the investigator/coordinator.

#### **4.11. Sample Storage and Shipment:**

There are no study related collections of blood samples or any other body fluids. If required, blood samples etc. will be collected and processed according to the routine procedures of the centers.

#### **4.12. Analysis Sets:**

The following analysis sets are defined.

Intent-To-Treat Analysis Set – Propensity Score Selected (ITT-PS Selected): The ITT-PS Selected analysis set will include all subjects enrolled into the study or control groups in which treatment was attempted as defined by the recording of incision time. Subjects will be classified by the group in which they are enrolled, regardless of whether or not that treatment was actually completed. Intraoperative failures will be included in primary hypothesis testing as composite clinical endpoint failures. Primary efficacy analyses will be conducted using the ITT – PS Selected analysis set. A subject must be selected into a PS subclass in order to be included in this analysis set. The PS subclassification procedure is designed to retain all subjects receiving the study device, if possible. Since selection into a PS subclass is the observational study equivalent to randomization in a randomized study, control subjects not selected into a PS subclass will not be included in the ITT – PS Selected analysis set and not included in primary effectiveness and safety analyses. Non-selected subjects are referred to as 'trimmed'. Safety data will be summarized separately for trimmed controls.

Completers Analysis Sets: Completers analysis sets will be defined at ITT-PS Selected evaluable for composite clinical success.

Safety Analysis Set: The Safety analysis set will include all subjects in the ITT-PS Selected analysis set plus study device patients who were not selected into a PS subclass, if any. Study device patients who were not selected into a PS subclass will be assigned to the subclass with the largest propensity scores for analyses that control for PS subclass. Primary safety analyses will be conducted using the Safety analysis set.

Per Protocol Analysis Set (PP): The PP analysis set will include subjects in the ITT-PS Selected analysis set with no major protocol violations of inclusion or exclusion criteria, as determined by

the Clinical Events Committee (CEC) and who are evaluable for the Month 24 composite clinical success endpoint (Objective 2, 3, and 4) or evaluable for the Month 60 CCS (Objective 1). It may also exclude subjects with confounding medical events or treatments following index surgery that are expected bias determination of the primary composite clinical success endpoint, as determined by the CEC. Secondary efficacy analyses will be conducted using the PP analysis set.

#### **4.13. Subject Discontinuation**

Patients which did not receive a patient number will be replaced – they will be judged as screening failures. At the end of the initial recruitment phase of 406 patients that fulfil all in-/exclusion criteria should be allocated to the study.

In order to meet 406 treated study patients those patients that are excluded by the investigator during the surgery will be replaced.

The patient is entitled to terminate the clinical investigation at any time without giving any reason and without having to expect any disadvantages by the Investigator.

Reasons for withdrawal of a patient from the clinical investigation may be:

- Insufficient cooperation of the patient (non-compliance with study procedures);
- Technical or administrative reasons (change of Investigator, move of the patient);
- Withdrawal of Informed Consent;
- Death

Pregnancy will not be a reason for discontinuation. The number of x-rays taken will be limited.

For patients who terminate the clinical investigation prematurely, a complete final examination has to be performed if the patient is still available for an examination.

For this final examination all assessments as planned for Visit 5 have to be carried out.

If the patient cannot come to a final examination the Investigator should clarify the reason and time point for discontinuation/drop out by phone and document this in the source document used at the site. In case of drop outs due to an (S)AE the Adverse Event has to be documented sufficiently in the SAE form and the Investigator has to report the SAE to the sponsor within 24 hours (see section about SAE reporting).

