## 7.11. Handling of Missing Data for Primary CCS Endpoints

### 7.11.1. Bayesian Multiple Imputation

To best preserve an intent-to-treat analysis, the testing of the primary Month 60 superiority hypothesis (Objective 1) will be done on the ITT-PS selected analysis set. Those subjects who withdraw, or who are lost to follow-up (LT FU) after enrollment will be included in the analysis using a modification of Bayesian multiple imputation to accommodate the PS subclass design. This analysis will be the primary analysis, but recognizing that there is no way, statistically, to handle these subjects without possibly introducing bias, a tipping point analysis will be also be conducted. For comparison purposes, a completers analysis will also be performed. The following describes the method. A similar method will be applied to analyses for other objectives.

In general, Bayesian Multiple Imputation (MI) may be employed to impute the expected status at Month 60 for patients who have not completed follow-up and have not been identified as “terminal failures”. Terminal failures include any event which is counted as a CCS failure no matter what happens after such an event occurs such as a secondary surgical invention. The imputation algorithm uses a beta-binomial distribution to model the transition probabilities from the outcome at month  $j$  to that at month 60, separately for the treatment and control groups. Specifically, the probability of a success for a subject in treatment group  $t$ , with last follow-up  $j$  and last follow-up value  $r$  can be described using a beta distribution:

$$\Pi_{p,t,j,r} \sim \beta(1 + S_{p,t,j,r}, 1 + F_{p,t,j,r})$$

Where  $p$  = propensity score subclass = {1, 2, 3, 4, 5}

$t$  = treatment group = {coflex=S, Decompression=D}

$j$  = follow-up time = {3, 6, 12, 24, 36, 48}

$r$  = success or failure status at time  $j$  = {1=success, 0=failure}

$\Pi_{p,t,j,r}$  = Month 60 success probability for subjects in subclass  $p$ , in treatment group  $t$ , who were successes ( $r=1$ ) or failures ( $r=0$ ) at follow-up time  $j$ .

$S_{p,t,j,r}$  = Number of Month 60 successes for subjects in subclass  $p$ , in treatment group  $t$ , who were successes ( $r=1$ ) or failures ( $r=0$ ) at follow-up time  $j$ .

 Guidance for Industry and FDA Staff Clinical Data Presentations for Orthopedic Device Applications Document issued on: December 2, 2004.

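### The rules for patients excluded during surgery conflict: 4.8.2 and 4.13 make them replaced dropouts, 4.12 and 7.2 score an undefined class of intraoperative failure, and leaving the excluded patients out could favour coflex

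*Combined protocol and SAP*

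**What the plan says.** Section 4.6 treats a patient as enrolled once consent is signed and the incision is made. Several later rules can then apply to a patient whom the surgeon finds unsuitable during the operation.

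- **Section 4.8.2** says "the surgeon has to exclude the patient from the trial participation" when a contradicting circumstance is found. It lists three possible reasons: instability requiring fusion, resection of disc tissue, and adverse events that prevent implantation ("S)AEs assessed during surgery that rule out the implantation of coflex"). It acknowledges that these patients had been enrolled and requires an eCRF, but limits what the monitor checks to consent, demographics and the reason. It adds: "The patient will be a dropout and the dropout reason will be recorded in the eCRF".
- **Section 4.13** says that, to reach the target of 406 treated patients, "those patients that are excluded by the investigator during the surgery will be replaced".
- **Section 4.12** defines the ITT-PS Selected set by a recorded incision time, whether or not treatment was completed, subject to selection into a PS subclass. "Intraoperative failures will be included in primary hypothesis testing as composite clinical endpoint failures".
- **Section 7.2** repeats that definition, but applies the scoring of intraoperative failures to primary non-inferiority testing only.
- **Section 7.11.1**: "Those subjects who withdraw, or who are lost to follow-up (LT FU) after enrollment will be included in the analysis", by multiple imputation, unless they are terminal failures. The imputation cells are indexed by PS subclass, arm, last follow-up time (3 months at the earliest) and status at that time.

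**The concern.** Nothing says which rule governs a patient excluded during surgery. Read one way, the patient is a CCS failure. Read another, the patient is a dropout to be imputed. Read a third way, the patient has left the trial and a new patient stands in.

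The choice may not be neutral between arms. An adverse event that rules out implanting coflex has no natural counterpart where no device is planned, and section 4.6 has each site enrol one arm only. If patients excluded for that reason are not counted as failures, failures specific to the device leave the coflex denominator. What is at stake is who counts as a failure in the primary test, and whether that is settled before outcomes are seen.

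**Working it through.** **1. Does section 4.12 already settle the matter?** Not fully, when the sections are set side by side.

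- *Intraoperative failure* is not defined, and no section equates it with exclusion during surgery.
- It is not among the Month 60 CCS components in 3.1, 3.2 or 5.1.
- Breakage of a spinous process is an example of an exclusion reason in 4.8.2, while 5.2.7 says a spinous process fracture is not a treatment failure.
- 4.12 applies the scoring to all primary hypothesis testing; 7.2 applies it to non-inferiority testing. Objective 1 is superiority.
- A patient with no postoperative visit has no imputation cell in 7.11.1, and no fallback is stated.

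**2. Reproducing the plan's Objective 1 figures.** Inputs: 150 per group (4.2); coflex Month 60 success 0.57 and coflex prior beta(82.1, 62.1) (7.7.1); control prior beta(1,1) (7.11.1); posterior threshold 0.95 (7.3). With s coflex and d control successes, the posteriors are

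π_S ~ beta(82.1 + s, 62.1 + 150 − s) and π_D ~ beta(1 + d, 1 + 150 − d).

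Superiority is concluded when P(π_S > π_D) ≥ 0.95. The probability of that conclusion is summed exactly over the two binomial distributions.

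- Power at 0.57 against 0.445: 82.3% (stated 83%).
- Power at 0.57 against 0.47: 64.7% (stated 65%).
- Type 1 error at 0.57 in both arms: 0.036 (stated 0.037, simulation SD 0.0011).

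The model is close enough to the plan's to measure a change.

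**3. Effect of leaving excluded patients out.** The documents give no exclusion rate, so a share x of 1% to 5% of coflex patients is assumed. Suppose true success is 0.57 in both arms when excluded patients count as failures. Dropping and replacing them moves the coflex rate to 0.57 / (1 − x); at 2%, 0.57 / 0.98 = 0.582. Imputing them at the rate of the remaining coflex patients gives the same expected rate. The power column takes the opposite handling: excluded patients are kept as failures and the others succeed at 0.57, so the coflex rate is 0.57 × (1 − x), against a control rate of 0.445.

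| x, coflex only | Patients of 186 | Coflex rate if dropped | Type 1 error if dropped | Power if kept as failures |
|---|---|---|---|---|
| 0% | 0 | 0.570 | 0.036 | 82.3% |
| 1% | 1.9 | 0.576 | 0.042 | 80.6% |
| 2% | 3.7 | 0.582 | 0.048 | 78.7% |
| 3% | 5.6 | 0.588 | 0.055 | 76.9% |
| 5% | 9.3 | 0.600 | 0.073 | 72.8% |

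Type 1 error passes 0.05 between 2% and 3%, about 4 to 6 of 186 coflex patients. With a Jeffreys prior for controls, as in 7.7.2, it runs from 0.035 at 0% to 0.072 at 5%.

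**4. Allowing for control exclusions.** Two of the three listed reasons can occur in either arm. If excluded controls are dropped as well:

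| Coflex exclusions | Control at half the coflex rate | Control at the coflex rate |
|---|---|---|
| 2% | 0.037 | 0.027 |
| 5% | 0.038 | 0.017 |

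At equal rates type 1 error falls below the baseline of 0.036, because both observed rates rise while the coflex prior still pulls that arm towards 0.57.

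**The case against.** The strongest reply is that the primary analysis as written already protects against this. Sections 4.12 and 7.2 define membership by incision time regardless of completion. Section 4.8.2 itself calls these patients enrolled. Replacement in 4.13 serves a recruitment target of 406 treated patients and removes nobody from an analysis set. A patient scored as a failure under 4.12 would also be a terminal failure under 7.11.1 and so not imputed. On that reading, coflex-specific exclusions count against the device.

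Much of this stands. A reader might infer that the plan's primary analysis is biased towards coflex. The documents do not support that: the bias arises only if the dropout and replacement rules are allowed to override 4.12, or if these patients are imputed, and no section says so. The device-related reason is also not expressly limited to one arm.

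A reader might also infer that later outcomes and safety data for these patients are not collected. That is too strong. An eCRF is completed; 4.13 asks for a final examination with the Visit 5 assessments where the patient is available, and for SAE documentation; 6.7 follows adverse events until resolved or explained; and the Safety set contains all ITT-PS Selected subjects. What is not stated is continued scheduled follow-up.

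The reply does not remove the conflict. It needs *intraoperative failure* to include every patient excluded during surgery, which no section says, and it needs 4.12 to prevail over 7.2 for the superiority objectives.

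**Conclusion.** The concern holds in a conditional form. The sections conflict, and the handling of a patient excluded after incision is left to discretion. If such patients are omitted or imputed instead of failed, and exclusions occur mainly in the coflex arm, Objective 1 type 1 error rises from 0.036 to 0.042 (1%), 0.048 (2%), 0.055 (3%) or 0.073 (5%). It barely moves if controls are excluded at half the coflex rate, and falls if the rates are equal.

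These figures rest on assumed exclusion rates, 150 analysed patients per group, and excluded patients otherwise counting as failures. They do not model the averaging over PS subclasses. They show that a handful of patients could matter; they do not show that the trial's error rate is inflated. The sections should be reconciled before outcomes are unblinded.

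**What to change.** Reconcile 4.8.2, 4.12, 4.13, 7.2 and 7.11.1:

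- Define *intraoperative failure* to include any patient excluded after incision.
- State that these patients stay eligible for PS selection and, if selected, remain in ITT-PS Selected in the arm in which they were enrolled. A rule that every incised patient stays in the set would contradict the planned trimming.
- State that they are terminal CCS failures for all objectives and are not imputed. In 7.2, replace the reference to non-inferiority testing with hypothesis testing, to match 4.12.
- State that replacements are additional enrolments and do not substitute for the excluded patient in the analysis.
- Keep these patients in scheduled study follow-up and adverse event collection.
- Report the number excluded during surgery by arm and reason.

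The cost is wording, follow-up visits for a few patients who have already consented, and a slightly less favourable coflex rate. With coflex-only exclusions, Objective 1 power would be about 79% at 2% and 73% at 5%, against 82% by the same calculation.
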